## 11. DESCRIPTION OF GLOBAL AMENDMENT(S)

### 11.1 GLOBAL AMENDMENT 1

Date of amendment	20Apr2021
BI Trial number	1245-0191
BI Investigational Medicinal Product(s)	Jardiance®, Empagliflozin BI 10773
Title of protocol	A phase III, randomised, double-blind, placebo-controlled, parallel group study of Empagliflozin (10 mg and 25 mg) administered orally once daily in combination with insulin with or without up to two oral anti-diabetic agents for 24 weeks in Chinese type 2 diabetic patients with insufficient glycemic control.
Global Amendment due to urgent safety reasons	
Global Amendment	
Section to be changed	Title page
Description of change	CTL information changed
Rationale for change	Team member hand over
Section to be changed	Synopsis
Description of change	Trial design, number of patients, inclusion criteria and statistical methods
Rationale for change	To be consistent with the sections 3.1, in the protocol.
Section to be changed	section 3.1
Description of change	Added Empagliflozin pooled doses in design and updated the total patient number
Rationale for change	To reflect the update in 7.2 planned analysis and 7.5 sample size calculation.
Section to be changed	section 3.3
Description of change	updated the total patient number and each treatment number
Rationale for change	To reflect the update in section 7.5 sample size calculation.
Section to be changed	section 3.3.2, section 4.2.1
Description of change	Inclusion criteria #3 is updaed “Acceptable basal insulins should have duration of action up to 24 h such as Insulin Degludec, insulin glargin, insulin detemir or NPH (neutral protamine hagedorn) insulin;”

Proprietary confidential information © 2021 Boehringer Ingelheim International GmbH or one or more of its affiliated companies

		Inclusion criteria #5, the SI unit for Fasting C-peptide is added
Rationale for change		To clarify better the acceptable basal insulins definition To be consistant with the unit in the lab report;
Section to be changed		section 3.3.4.1
Description of change		Added one more criteria of treatment discontinuation: The patient experiences an infection with SARS-CoV-2. The patient may resume trial treatment following recovery from SARS-CoV-2 infection if the patient is expected to derive clinical benefit, as agreed between the investigator and sponsor. Removed “as run-in failure” from “They have to be recorded in eCRFs and no further follow-up is required (except for AEs, if needed).”
Rationale for change		COVID-19 pandemic; To consistent with eCRF form.
Section to be changed		section 4.1.4
Description of change		To ensure a dose interval of about 24 hours, the medication is proposed to be taken at the same time every day.
Rationale for change		To clarify the medication taken time requirement which is not at the exact same time every day for actual practise.
Section to be changed		section 4.2.1
Description of change		added the adverbial clause in “The total prescribed insulin dose should not be changed by more than 10% of the baseline value in the 24 weeks after randomisation unless rescue therapy criteria for treatment hyperglycemia are met or in case of hypoglycemia requiring insulin dose reduction beyond the defined limits.”
Rationale for change		To clarify the insulin dose is allowed to change under the specific condition as described in the same section.
Section to be changed		section 5.1
Description of change		Site should contact patients in advance to remind the conduction of the test. The timing of the 8-point blood glucose measurement is proposed as follows

Proprietary confidential information © 2021 Boehringer Ingelheim International GmbH or one or more of its affiliated companies

Rationale for change	To clarify better the requirement for the 8-point glucose measurement.
Section to be changed	section 6.2.1
Description of change	If the HBGM test reveals an overnight fasted blood glucose of >240 mg/dl (>13.3 mmol/l), the patient should contact the study site for a visit at the next day.
Rationale for change	To correct typo in the unit
Section to be changed	Section 7.2.2.1
Description of change	In MMRM, the response variable HbA1c change from baseline at week 24 were changed HbA1c change from baseline to at each on-treatment visit.
Rationale for change	To correct the typo in the response variable.
Section to be changed	Section 7.2.2.4
Description of change	Added supplementary analysis to explore the efficacy of empagliflozin pooled doses (10 mg + 25 mg) against placebo.
Rationale for change	To better address the scientific question whether Empagliflozin is efficacious as add-on to insulin in Chinese patients with T2DM.
Section to be changed	Section 7.5
Description of change	The estimated difference between Empagliflozin (10 mg q.d., 25 mg q.d.) and placebo in the change in HbA 1c from baseline at week 24 is updated to 0.62% and 72 (instead of 91) patients per treatment arm and a total of 216 patients are needed.
Rationale for change	A study of Empagliflozin as add-on to insulin in Japanese patients with T2DM has shown a more pronounced effect.
Section to be changed	section 8.3.2
Description of change	Added the extra access to source data and documents: In the event of force majeure or other disrupting circumstances (e.g. pandemic, war, please see section 6.1), site access may be restricted thus limiting the ability to perform standard site monitoring activities on site such as on-site source data review and source data verification. Therefore, some of these activities may be

Proprietary confidential information © 2021 Boehringer Ingelheim International GmbH or one or more of its affiliated companies

	performed remotely or replaced by centralized monitoring to the extent possible, based on a documented risk assessment and in alignment with local regulations.
Rationale for change	COVID-19 pandemic
Section to be changed	Section 9.1
Description of change	Published reference P19-10212 is added.
Rationale for change	As reference for the updated estimated treatment difference.
Section to be changed	Section 1.4.2
Description of change	
Risk evaluation in relation with COVID-19 added:
 
Patients with serious underlying medical conditions such as T2D are at higher risk for severe illness from coronavirus disease 2019 (COVID-19). Therefore, in case of local high risk of COVID-19 infection, on-site visits may not be carried out. In the event of restriction to visit the investigator site, a remote visit can be performed. This change is meant to keep the integrity of the trial and it will not affect the assessment of benefit-risk of empagliflozin.
 
There is no indication that empagliflozin may increase the risk of COVID-19 infection. As with any acute illness, empagliflozin during COVID-19 infection has the potential to increase the risk of diabetic ketoacidosis. The risk of diabetic ketoacidosis in case of acute illness is adequately addressed in the IB and in the patient information and consent form.
 
In case of a confirmed COVID-19 infection, trial treatment will be discontinued.

Rationale for change	COVID-19 pandemic
Section to be changed	Flow Chart, Section 4.1.4, 6.1, 8.1 and 10.2;
Description of change	Contingency measures have been introduced to ensure patient safety and appropriate trial continuation based on a thorough benefit risk assessment (see Section 1.4.2) and above. Introduce flexibility for trial visits: to allow in exceptional cases visits to be done as remote visits; to allow for IMP shipment from site to

Proprietary confidential information © 2021 Boehringer Ingelheim International GmbH or one or more of its affiliated companies

	patient in this case. Patients need to agree to changes prior to them being implemented. Comment added below the Flow Chart to refer to the contingency measures if they are needed.
Rationale for change	COVID-19 pandemic

2 LIST OF ABBREVIATIONS

Term	Definition / description
AE	Adverse event
AESI	Adverse event of special interest
ALQ	Above Limit of Quantification
ALT	Alanine transaminase
ANCOVA	Analysis of covariance
ASA	Acetylsalicylic acid
AST	Aspartate transaminase
ATC	Anatomical-Therapeutic-Chemical classification
BI	Boehringer Ingelheim
BIcMQ	BI-customised MedDRA query
BLQ	Below Limit of Quantification
BMI	Body mass index
CEC	Clinical event committee
CRF	Case report form
CT	Concomitant therapy
CTP	Clinical Trial Protocol
CTR	Clinical Trial Report
DBP	Diastolic blood pressure
DKA	Diabetic Ketoacidosis
ECG	Electrocardiogram
eCCr	Estimate creatinine clearance
eGFR	Estimated glomerular filtration rate
EoT	End of treatment
FPG	Fasting plasma glucose
FPI	Fasting plasma insulin
HbA1c	Glycated haemoglobin
HOMA-IR	Homeostatic model assessment - insulin resistance
HOMA- β	Homeostatic model assessment - β
ICH	International Conference on Harmonisation
IPD	Important protocol deviation
IRT	Interactive Response Technology

Proprietary confidential information © 2021 Boehringer Ingelheim International GmbH or one or more of its affiliated companies

Term	Definition / description
LOCF	Last observation carried forward
LQ	Limit of Quantification
MDRD	Modification of Diet in Renal Disease
MedDRA	Medical Dictionary for Regulatory Activities
MI	Multiple imputation
mITT	Modified intention to treat
MMRM	Mixed-effect Model Repeated Measures
MQRM	Medical Quality Review Meeting
MTT	Meal tolerance test
NCF	Non-completers considered failure
OAD	Oral antidiabetic drug
OC	Observed case
OC-AD	Observed cases – all data
OR	Original results
PK	Pharmacokinetics
PPG	Post parandial glucose
PPS	Per protocol set
PT	Preferred term
PD	Protocol deviation
Q1	Lower quartile
Q3	Upper quartile
REML	Restricted maximum likelihood
RPM	Report planning meeting
SBP	Systolic blood pressure
SCR	Screened set
SAE	Serious adverse event
SD	Standard deviation
SDL	Subject data listing
SMQ	Standardised MedDRA query
SOC	System Organ Class
TOC	Table of contents
TSAP	Trial statistical analysis plan

Proprietary confidential information © 2021 Boehringer Ingelheim International GmbH or one or more of its affiliated companies

Term	Definition / description
UACR	Urine albumin-to-creatinine ratio
ULN	Upper limit of normal
UTI	Urinary tract infection

Proprietary confidential information © 2021 Boehringer Ingelheim International GmbH or one or more of its affiliated companies

3 INTRODUCTION

As per ICH E9, the purpose of this document is to provide a more technical and detailed elaboration of the principal features of the analysis described in the protocol, and to include detailed procedures for executing the statistical analysis of the primary and secondary variables and other data.

This trial statistical analysis plan (TSAP) assumes familiarity with the Clinical Trial Protocol (CTP), including Protocol Amendments. In particular, the TSAP is based on the planned analysis specification as written in CTP Section 7 “Statistical Methods and Determination of Sample Size”. Therefore, TSAP readers may consult the CTP for more background information on the study, e.g., on study objectives, study design and population, treatments, definition of measurements and variables, planning of sample size, randomization.

SAS® Version 9.4 or later version will be used for all analyses.

Proprietary confidential information © 2021 Boehringer Ingelheim International GmbH or one or more of its affiliated companies

4 CHANGES IN THE PLANNED ANALYSIS OF THE STUDY

There are no changes in this TSAP compared to the statistical methods described in the CTP.

Proprietary confidential information © 2021 Boehringer Ingelheim International GmbH or one or more of its affiliated companies

5 ENDPOINTS

5.1 PRIMARY ENDPOINT

The endpoint will be used as defined in CTP Section 2.1.2.

[figure not shown]
5.2 SECONDARY ENDPOINTS

5.2.1 Key secondary endpoints

[figure not shown]
Since there are no key secondary endpoints specified in the CTP, this section is not applicable.

5.2.2 Other secondary endpoints

The endpoints will be used as defined in CTP Section 2.1.3.

Proprietary confidential information © 2021 Boehringer Ingelheim International GmbH or one or more of its affiliated companies

6 GENERAL ANALYSIS DEFINITIONS

6.1 TREATMENTS

There will be five treatment study phases in this trial: screening, placebo run-in, double-blind study treatment phase (with empagliflozin and matching placebo), post-treatment and post-study.

Table 6.1:1 Treatment regimens / study intervals

Label	Interval	Start date	Start time
Screening	Screening	Date of informed consent	00:00
Run-in	Run-in	Date of first administration of run-in medication	Time of first administration of run-in medication, 12:00 if missing
Placebo/ Empagliflozin 10mg/ Empagliflozin 25mg	Treatment	Date of first administration of double-blind study medication	Time of first administration of double-blind study medication, 12:00 if missing
Post-treatment	Post-treatment	Date of last intake of study medication +X+1 (see definition of X below)	00:00
Post-study	Post-study	Start date= Last contact date, defined as the maximum of (Trial completion date, last study medication intake + X) +1	00:00

The purpose of the definitions above is to describe all the different study/treatment intervals, to which a patient can be assigned during the course of the trial. Note that the term “treatment regimen” can also cover time periods with no active treatment.

In general, for safety analyses, data up to 7 days after last study medication intake will be considered as on-treatment for AEs, 3 days for laboratory values and 1 day for pulse rate: To clarify:

- Pre-treatment: before the first intake of any study medication.
- On treatment: begins from the date of first administration of the initial randomised study medication to last intake of study medication + X days (inclusive), where X=1, 3 or 7 days for pulse rate, safety laboratory, and AE respectively.

Proprietary confidential information © 2021 Boehringer Ingelheim International GmbH or one or more of its affiliated companies

- Post-treatment: begins from the last intake of study medication + X days + 1 day up to the last contact date (inclusive). Last contact date is defined in [Table 6.1:1](#). Post treatment period is not applicable for patients with last contact equal to 'last intake + X + 1 days' where X is 1, 3, or 7 days as previously specified.
- Post-study: From day after last contact defined in [Table 6.1:1](#). If period starts at end of on-treatment period, then post-treatment period is not applicable.

For efficacy analyses, data up to 7 days after last treatment intake will be considered as on-treatment for HbA_{1c} and waist circumference and 1 day for all other efficacy endpoints. For further details, see [Table 6.7:1](#).

The efficacy analyses will follow the intention-to-treat (ITT) principle in assigning patients to treatment groups, i.e. patients will be analysed in the treatment group they were randomized to.

Safety analyses will assign patients to the treatment group as initially treated.

In addition, AEs with an onset during the time of the incorrect study treatment will be listed separately.

6.2 IMPORTANT PROTOCOL DEVIATIONS

Not all important protocol deviations (IPDs) will generate exclusion from the per protocol population. Deviations that lead to exclusion from analysis populations are indicated as such in [Table 6.2:1](#).

IPD definitions will include consideration of, among others, important deviations of entry criteria, treatment non-compliance, treatment dispensing errors, prohibited concomitant medication and premature unblinding.

The decision about which protocol deviation (PD) could generate exclusion from analysis sets will be taken during the course of the study and finalised at the last report planning meeting (RPM), i.e. before unblinding.

The following table defines the different categories of IPDs. The final column describes which analysis set will the patients be excluded from.

Proprietary confidential information © 2021 Boehringer Ingelheim International GmbH or one or more of its affiliated companies

Table 6.2:1 Important protocol deviations

IPD Code	IPD Category & brief description	Example/Comment	Exclude from which analysis set
A	Entrance criteria not met		
A1	Target indication not met		
A1.01	No type 2 diabetes	Inclusion criterion #2 not met	PPS
A1.02	Antidiabetic background therapy not as required	Inclusion criterion #3 not met	PPS
A2	Inclusion criteria not met		
A2.01	HbA1c out of range	Inclusion criterion #4 not met	PPS
A2.02	Age out of range	Inclusion criterion #1 not met	None
A2.03	Body mass index out of range	Inclusion criterion #6 not met	None
A2.04	Fasting C-peptide out of range	Inclusion criterion #5 not met	None
A3	Exclusion criteria met		
A3.01	Uncontrolled FPG level	Exclusion criterion #4 met	None
A3.02	Additional background therapy	Exclusion criterion #2, #9, #11, #12, #14 met	PPS
A3.03	Relevant concomitant diagnoses	Exclusion criterion #1, #6, #7, #20, #23 met	None
A3.04	Bariatric or other relevant gastrointestinal surgery within the past two years	Exclusion criterion #8 met	PPS
A3.05	Blood dyscrasias or any disorders causing hemolysis or unstable red blood cell count	Exclusion criterion #15 met	PPS
A3.06	Indication of liver disease	Exclusion criterion #13 met: ALT or AST or alkaline phosphatase > 3xULN at V1	None
A3.08	Treatment with protocol excluded anti-obesity drugs	Exclusion criterion #10 met	PPS
A3.09	Renal insufficiency or renal impairment (assessed by eGFR)	Exclusion criterion #3 met	PPS
A3.10	Treatment with protocol excluded systemic steroids or recent change in thyroid hormone dose	Exclusion criterion #16, #17 met	PPS
A3.11	Relevant alcohol or drug abuse and other conditions affecting study compliance	Exclusion criterion #18 met	PPS
A3.12	Any other clinical condition unsafe for participation that would jeopardise patient safety while participating in this clinical trial	Exclusion criterion #5, #22, #24, #25, #26 met	None
A3.13	Renal insufficiency or renal impairment (assessed by eCcR)	Exclusion criterion #19 met	PPS
A3.14	Known allergy or hypersensitivity to empagliflozin or other SGLT-2 inhibitors	Exclusion criterion #21 met	None

Proprietary confidential information © 2021 Boehringer Ingelheim International GmbH or one or more of its affiliated companies

Table 6.2 :1 Important protocol deviations (cont.)

IPD Code	IPD Category & brief description	Example/Comment	Exclude from which analysis set
A3.15	Women who are pregnant, nursing, or who plan to become pregnant while in the trial.	Exclusion criterion #27 met	None
B	Informed Consent		
B1	Informed consent not available/not done	Inclusion criterion #7 not met	All
B2	Informed consent too late	Date of informed consent not obtained prior to any study related procedure. Minimum requirement <= date of Visit 1/date of any study procedure	None
C	Trial medication and randomisation		
C1.01	No study medication taken	Patient randomised according to IRT system but no medication taken according to eCRF/IVRS	TS, mITT, PPS
C1.02	Incorrect trial medication taken	Wrong medication taken, i.e. eCRF kit number does not match kit number assigned by IVRS* [Needs unblinding to determine if kit was same medication as assigned or not – so, will be finally judged after DBL]	PPS
C2.01	Treated without randomisation	Patient treated according to eCRF, but not randomised according to IVRS	mITT, PPS
C3.01	Non-compliance with study drug intake	Overall study compliance outside 80% and 120% (exclusive) or study treatment compliance below 80% in the last visit interval before primary endpoint assessment. [Final decision at the DBL meeting based on medical judgement.]	PPS
C4.01	Medication code broken at site without just cause	Medication code was broken for no valid reason.	PPS
D	Concomitant medication		
D2.01	Background antidiabetic therapy not taken as specified in the protocol	Review of eCRF for prohibited medication and check whether other than protocol defined rescue medication was taken* [Final decision at the DBL meeting based on medical judgment]	PPS
E	Missing data		
E1.01	No baseline HbA1c value	No valid baseline HbA1c value	mITT, PPS

6.3 SUBJECT SETS ANALYSED

The following analysis sets will be defined for this trial.

- *Screened patients set (SCR):*

Proprietary confidential information © 2021 Boehringer Ingelheim International GmbH or one or more of its affiliated companies

This patient set includes all patients screened for the trial, with informed consent given and who completed at least one screening procedure at Visit 1.

- *Treated set (TS):*

This patient set includes all patients who are randomized and treated with at least one dose of study medication. The assignment of patients to treatment groups will be based on the actual first study medication intake in the double-blind treatment period. The TS is the basis for safety analyses.

- *Modified Intention-to-Treat (mITT) set:*

This patient set includes all randomized patients who are treated with at least one dose of the study medication and have a baseline HbA1c assessment and at least one on treatment HbA1c value. The assignment of patients to treatment groups will be based on the planned randomised study medication at the time of randomisation. The primary efficacy analysis will be performed on mITT set with patients who have a baseline HbA1c and at least one on treatment HbA1c measurement during randomized period.

- *Per-protocol set (PPS):*

This patient set includes all patients in the mITT set who do not have any important protocol deviations (iPDs) which can be expected to have a distorting influence on the assessment of the primary endpoint. iPDs are detailed in [Table 6.2:1](#).

In [Table 6.3:1](#) the data sets which are to be used for each category class of endpoint are illustrated.

Proprietary confidential information © 2021 Boehringer Ingelheim International GmbH or one or more of its affiliated companies

Table 6.3:1 Summary of which data sets will be used for which class of endpoints

[figure not shown]
Class of endpoint	Subject sets			
	SCR	TS	mITT	PPS
Disposition	OR			
Demographics		OR		
Baseline variables		OR		
Background total daily insulin dose/concomitant medications		OR		
Concomitant diagnoses/relevant medical history		OR		
Exposure/compliance		OR		
Primary endpoints			Primary analysis (OC) & Secondary analyses (MI, OC-AD)	OC
Secondary and further efficacy endpoints-continuous			OC, OR#	
Secondary and further efficacy endpoints-binary			NCF	
Subgroup analyses			OC	
Safety endpoints		OR		

SCR=screened set, mITT set=modified intention-to-treat set, PPS=per protocol set, TS=treated set; patient sets are defined in Section 6.3

[figure not shown]
OR=original results, OC=observed cases on treatment, OC-AD=observed cases-after discontinuation and rescue therapy, NCF=Non-completers considered failures. Handling of missing data is described in [Section 6.6](#)

[figure not shown]
#OR results will only be presented for time to first rescue medication and number of patients with rescue.

“OK results will only be presented for time to first rescue medication and number of patients with rescue.”

Proprietary confidential information © 2021 Boehringer Ingelheim International GmbH or one or more of its affiliated companies

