##### **Modified Intention-to-Treat (mITT) set**

The mITT set will consist of all randomized patients who are treated with at least one dose of the study drug and have a baseline HbA1c assessment. The assignment of patients to treatment groups will be based on the planned randomised study drug at the time of randomisation.

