##### *Analysis of effectiveness*

The analysis of the primary endpoint will be repeated on the mITT set but include all on- and off-treatment (i.e. measured after premature discontinuation of study drug or after rescue therapy is initiated) HbA1c values using the same MMRM model as for the primary analysis to assess the effectiveness of the study drug.

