### **7.3 HANDLING OF MISSING DATA**

For the analysis of the primary endpoint, the handling of missing data is described in [section 7.2.2.](#)

For percentage of patients with  $\text{HbA}_{1c} < 7.0\%$  after 24 weeks of treatment, the missing data will not be imputed. Patients who prematurely discontinue the treatment or initiate rescue therapy will be treated as non-responder (i.e.,  $\text{HbA}_{1c} \geq 7.0\%$  after 24 weeks of treatment).

No imputation for missing data will be performed for secondary efficacy endpoints of change from baseline in body weight, SBP, DBP and FPG. The missing data will be handled by MMRM model based on a likelihood method under the "missing at random" assumption.

Baseline Observation Carried Forward (BOCF) approach will be used for 2-hour PPG in ANCOVA analysis.

Missing or incomplete AE date will be imputed according to BI standards. Other missing safety data will not be imputed.

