6.6.2 Methods of data selection

Original result (OR) analysis

Original result analysis implies the analysis of data exactly as observed. OR analysis will be performed on endpoints that are either not affected by patients' antidiabetic rescue medication use or if it is not meaningful to apply any imputation rule on them for replacing the missing values.

Observed cases (OC) analysis

For all efficacy endpoints, it is planned to analyse only the available data that were observed while patients were on treatment, i.e., excluding the missing data. In other words, OC analysis will be performed and missing data in this analysis will not be replaced.

For all efficacy endpoints, this OC-technique will set all values measured after antidiabetic rescue medication taken to missing (antidiabetic rescue medication as defined in [section 6.6.1](#)).

Observed cases analysis including data after treatment discontinuation and rescue therapy (OC-AD)

To mimic an intent-to-treat (ITT) analysis, post-treatment as well as post-rescue measurements may also be included. This will be done as a secondary analysis of the primary endpoint with OC as the imputation rule.

Non-completers considered failure (NCF)

For binary endpoints, like a treat to target response of $\text{HbA1c} < 7.0\%$, a conservative method to replace missing values is to consider them as "failures". Missing data due to early discontinuation per the completer definition will be replaced as "failure" (i.e. $\text{HbA1c} \geq 7.0\%$) up to the planned final visit to be reached by all patients. Values obtained after rescue medication was started are also replaced as "failure".

A multiple imputation (MI) approach will also be used as a sensitivity analysis for the primary endpoint. Further details can be found in [Section 7.4.2](#).

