7.5.2.1 Responder analysis

The HbA1c responder analyses will be performed on mITT (NCF) by determining the percentage of patients that fulfil responder criteria (for the definition of treat to target and relative efficacy response, see [Section 5.2.2](#)) by treatment. Non-completers considered failures (NCF) imputation-technique will be used to impute the missing data for this analysis strategy.

Each analysis will consist of a tabulation by treatment of the percentage of patients meeting the response criteria along with 95% exact confidence intervals for the percentage. Additionally, a logistic regression model with treatment, background therapy, baseline eGFR and continuous HbA1c will be fitted on the binary response variable to calculate the estimate of the odds ratio of each dose to placebo. Estimate of odds ratios and 95% confidence intervals (Wald) will be presented along with the p-values for each comparison.

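### SAP 6.3 narrows the protocol's mITT set without declaring it, which drops some early discontinuers from the HbA1c responder denominator

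*SAP*

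**What the plan says.** Protocol 7.2.1 sets three conditions for mITT: randomised, "treated with at least one dose of the study drug and have a baseline" HbA1c. It asks for nothing after baseline.

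SAP 6.3 adds a fourth. Patients must "have a baseline HbA1c assessment and at least one on treatment HbA1c value". It repeats the condition for the primary analysis: "The primary efficacy analysis will be performed on mITT set with patients who have a baseline HbA1c and at least one on treatment" HbA1c measurement. SAP 4 states: "There are no changes in this TSAP compared to the statistical methods described in the CTP".

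For HbA1c, SAP 6.1 and Table 6.7:1 count a value as on treatment if it is taken after the first dose and no later than 7 days after the last.

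SAP 7.5.2.1 and Table 6.3:1 run the responder analysis on mITT with the non-completers-considered-failure (NCF) rule. SAP 7 bases percentages on all patients in the set, with or without a value. On early stoppers the two documents agree. Protocol 7.3: "Patients who prematurely discontinue the treatment or initiate rescue therapy will be treated as non-responder". SAP 6.6.2: "Missing data due to early discontinuation per the completer definition will be replaced as" failures.

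The protocol's effectiveness analysis (OC-AD in the SAP) also uses mITT: "The analysis of the primary endpoint will be repeated on the mITT set but include all on- and off-treatment" values.

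**The concern.** Under the SAP wording, membership of the set depends on something that happens after randomisation: whether the patient gave a blood sample in time. A treated patient with a baseline HbA1c who stops before the first post-baseline sample and misses a timely end-of-treatment sample is in the protocol's mITT but not in the SAP's.

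For the responder endpoint this works against the NCF rule. The rule exists to keep such patients in the denominator as failures, and the set definition takes them out before it can act. Removing failures cannot lower an arm's responder rate. If the arms lose different numbers, the odds ratio shifts, and the direction depends on which arm loses more.

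OC-AD has a smaller exposure. A patient whose only post-baseline HbA1c was taken off treatment would contribute to it under the protocol's set but is excluded under the SAP's. A patient with no post-baseline HbA1c at all adds nothing to it under either definition.

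A reader who relies on SAP 4 would not know that the set had changed.

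**Working it through.** **1. Is the definition really different?** Yes. Three conditions in the protocol became four in the SAP, and both texts are current. Table 6.2:1 gives some support to the protocol's version. Apart from missing consent, its only entries that exclude from mITT are no drug taken (C1.01), not randomised (C2.01) and no baseline HbA1c (E1.01). None covers a missing on-treatment HbA1c.

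**2. Who is lost?** HbA1c is drawn at every visit except Visit 2 (Protocol 5.1), and the end-of-treatment visit is due within 7 days of stopping (Protocol 6.2.2). Most early stoppers therefore stay in. Those lost mainly stop before the Week 4 sample, or before a later first sample if early visits were remote (Protocol 6.1), and then do not return in time.

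**3. Does the sample size depend on this?** No. With a difference of 0.62, SD 1.1 and two-sided alpha 0.05, the noncentral t distribution gives 68 per arm as the smallest number with 90% power. Power at 68 is 90.4% (stated: 90.3%). Inflation is 68/(1 − 0.08 × 0.6) = 71.4, rounded up to 72, and 3 × 72 = 216. The plan's figures are reproduced.

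**4. How many could be lost per arm (k)?** The documents do not say. The planning averages only show which values are arithmetically compatible, if no remaining censored patient counts as more than one completer.

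- 8% censoring: 0.08 × 72 = 5.76 patients, worth 5.76 × 0.4 = 2.304 completers. With k = 3 contributing nothing, the rest average 2.304/2.76 = 0.83. With k = 4 they would average 2.304/1.76 = 1.31, which is not possible.
- 15% censoring (Table 7.5:1): 0.15 × 72 = 10.8 patients, worth 4.32. With k = 6 the rest average 4.32/4.8 = 0.90. With k = 7 they would average 4.32/3.8 = 1.14, which is not possible.

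So k = 3 and k = 6 are used as illustrations. They are not estimates or bounds, and k = 0 is equally compatible.

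**5. Effect on the responder rate.** The rate is r/(72 − k), so it rises by the factor 72/(72 − k): 4.3% relative for k = 3 and 9.1% for k = 6. With an assumed 20 responders: 20/72 = 27.8%, 20/69 = 29.0%, 20/66 = 30.3%.

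**6. Effect on the unadjusted odds ratio**, [a/(72 − kₐ − a)] / [p/(72 − kₚ − p)], where a and p are assumed responders on active and placebo:

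| a v p | No loss | Active loses 3 | Placebo loses 3 | Active loses 6 | Placebo loses 6 |
|---|---|---|---|---|---|
| 10 v 5 | 2.16 | 2.27 | 2.06 | 2.39 | 1.97 |
| 20 v 10 | 2.38 | 2.53 | 2.27 | 2.70 | 2.15 |
| 30 v 15 | 2.71 | 2.92 | 2.57 | 3.17 | 2.43 |

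For example, (20/52)/(10/62) = 2.38 and (20/49)/(10/62) = 2.53. With equal loss at 20 v 10, the odds ratio is 2.41 (3 from each arm) or 2.43 (6 from each).

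**7. Effect on OC-AD.** Suppose all k lost active patients did return off treatment and had kept none of the benefit. A simple mean difference of 0.62 would then be overstated by 0.62 × k/72: 0.026 for k = 3 and 0.052 for k = 6. If they had kept all of it, the overstatement is 0.

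**The case against.** The strongest reply is that very little turns on this, and much of that stands.

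- **The primary analysis.** A patient with no on-treatment HbA1c supplies no response record to a model that uses on-treatment values only. The added condition does not practically change the contrast. By the same token, it gains nothing there.
- **The responder denominator.** Protocol 7.2.3 and 7.3 name no set for this endpoint, and 7.2.3 leaves further detail to the SAP. So no stated responder denominator is overridden. The SAP did choose mITT, however, and under the protocol's meaning of that label these patients would count.
- **The illustrations.** The 8% and 15% rates include rescue. Rescued patients are mostly not the ones lost: Protocol 4.2.1 asks for an HbA1c before rescue unless one was sent in the previous 4 weeks, and SAP 6.7 defines on-treatment by time, so a post-rescue value also satisfies the condition. Protocol 3.3.4.1 further asks for the end-of-treatment visit before any new antidiabetic drug. The realistic number is likely to be at the low end, and the one-sided losses of 6 are strained.
- **OC-AD.** The SAP sections that would detail the secondary analyses of the primary endpoint are not in the public copy. The point rests on Protocol 7.2.2.2 and SAP Table 6.3:1, which both name mITT.
- **Status and transparency.** The responder endpoint is outside the confirmatory hierarchy, and SAP 7 will report set sizes by arm. Reporting sizes does not put the failures back or correct SAP 4.

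**Conclusion.** The concern holds as a minor point. The SAP redefines mITT, says it has changed nothing, and thereby takes out of the responder analysis some patients whom both documents' missing-data rules count as failures.

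The size is unknown and probably small. A balanced loss barely moves the odds ratio. A one-sided loss of 3 per arm moves it by roughly 0.1 to 0.2 in the scenarios shown. These figures rest on assumed responder counts, assumed losses, 72 patients per arm and no covariate adjustment. The effect on OC-AD concerns fewer patients still. The primary estimate, the power and the order of testing are practically untouched.

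**What to change.** In SAP 6.3, delete the on-treatment HbA1c condition and the matching sentence about the primary analysis, so that mITT equals Protocol 7.2.1. Run the NCF responder analysis and OC-AD on that set.

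If the condition is kept for the primary model, declare it in SAP 4, give it its own flag instead of the mITT label, and report by arm how many patients it removes.

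At the same time, align one cell of SAP Table 6.3:1. It lists multiple imputation under mITT, whereas Protocol 7.2.2.2 bases that analysis on all randomised patients with a baseline HbA1c. SAP 7.4.2 is not in the public copy and may already state this, so no error in that analysis is claimed.

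The cost is SAP wording and one population flag. Responder rates may come out slightly less favourable.
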